Exclusions: We will exclude patients who cannot speak English. In future work, we plan to make a Spanish version if this version is deemed acceptable. We will exclude patients with cognitive impairment as determined by ability to provide informed consent. We will also exclude patients on isolation precautions due to resistant bacteria or impaired immune function.

C. Study Design and Research Methods

Settings: For this pilot, we will recruit from Denver Health Medical Center and UCHealth. At each site, we will recruit patients from both the inpatient and outpatient palliative care services and the outpatient geriatric and primary care clinics. In order to get perspectives on feasibility of the PtDA in populations at different places in their illness trajectory. We plan to recruit 120 patients (**Figure 1**).

Hundreds of patients each year who meet our eligibility criteria are served in each setting, so we will have no difficulty recruiting 20-25 patients from each site/setting.

[figure not shown]

Figure 1. Recruitment

Recruitment: Patients will be identified differently in each setting:

- **In the outpatient setting,** potential patients will be identified through weekly chart reviews. The study team will communicate with the outpatient physician by his/her preferred communication method (e.g. email, phone) to determine whether the patients are appropriate to be approached. Reasons for non-approach will be recorded. If eligible and appropriate, a research team member will approach the patient and introduce the study following their clinical encounter.
- **In the inpatient settings,** the study team will speak with the palliative care teams twice a week to identify eligible patients who are currently being followed by the consult service. Then, a member of the study team will contact the attending physician of record for the patient to determine if he or she has concerns with the patient being approached regarding enrollment in the study. If eligible and appropriate, a research team member will approach the patient and introduce the study.

Research Methods: This will be a patient-level trial randomized in a 2:1 intervention: control (see figure 1 above).

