- **Control - No PtDA:** Patients assigned to the control group will receive usual care. On the palliative care service, this typically includes a team with a physician, an advanced practice nurse, and occasionally other team member including a chaplain or a social worker. This consultation typically includes a discussion of advanced directives, symptoms, and prognosis. In the primary care settings, this is more variable and is a function of the primary care physician's practice and the patient's clinical situation.

- **Intervention - PtDA:** In addition to usual care, patients assigned to the intervention group will also be asked to view the hospice-PtDA. In the inpatient setting, the PtDA can be utilized anytime in the course of their hospitalization (all hospital rooms have a DVD player for the video). This could be before, during, or after the palliative care team consultation. In the outpatient setting, the patient will receive the PtDA after a clinic visit and will be allowed to take it home. In both settings, we have chosen a model with the PtDA delivery facilitated by research staff. The staff will NOT sit with patients while they watch the PtDA, as to allow patients to declare their desired use without study staff influence.

Data collection: For patients who agree to participate, the study coordinator will collect baseline demographic and quantitative data (surveys described above in Section A). The research coordinator will then open the envelope to determine the patient's allocation. Control patients will be asked to complete the baseline measures at time of enrollment and again at 1-month follow-up. Intervention patients will be given the decision aid and asked to review it within the next week. Then the best way to contact them 1 week later will be recorded (for outpatients, this will likely be at home by phone, for inpatients, this will likely be in the hospital.) Then the baseline surveys will be administered again by phone. Finally, each participant (control and intervention) will be contacted at one month for the final data point collection. \$25 gift cards will be given for baseline and one-month follow-up surveys.

- **Baseline visit (control & Intervention)-** All participants will be asked to complete the Hospice Knowledge Test, Decisional Conflict Scale, Decision Self-efficacy scale, SPMSQ, HADSA, PHQ-9 and demographics.

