- **1 week Follow-up call (intervention only)-** Participants will be asked to complete the Hospice Knowledge Test, Decisional Conflict scale, Decision Self-efficacy scale and brief qualitative survey.
- **One Month Follow-up (control & intervention)-** At one month follow-up all participants will be asked to complete the Hospice Knowledge Test, Decisional Conflict scale and the Decision Self-efficacy scale.

D. Description, Risks and Justification of Procedures and Data Collection Tools:

The study team believes that this project poses minimal risk to all subjects involved. The intervention involves review of decisional support materials and a series of quantitative and qualitative questions. Data collection from participants includes questions and medical record review to screen for eligibility and only limited demographic data will be obtained. Audio-recordings of all qualitative will be kept on a secure server on the University network to which only the study to will have access. There is always a risk that participants may feel uncomfortable discussing hospice or end-of-life decisions. Participants will be informed of their right to refuse to answer any question they do not wish to answer, and may terminate participation in the study at any point (and that should they decline to participate, answer a question or withdraw this will not affect their medical care).

Data collection and storage has been planned to appropriately protect participant confidentiality. All patients will be given a unique identification number, and study data and identifiable information will always be kept separate. REDCap, the COMIRB-preferred system, will be used to store all survey and enrollment data, and the University's secure server will be used to store clinic audio files, interview audio files, transcripts and notes; access to both REDCap and the secure server will be limited to study personnel only. All paper documents will be stored in a secure and locked file cabinet in a secure and locked office building – again, all study data paperwork will be stored separate from paperwork with identifiable information (i.e. signed consent forms) and be accessible to study personnel only.

E. Data Analysis Plan:

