Qualitative Data: The open-ended qualitative question will be analyzed using inductive and deductive content analysis.⁴⁰⁻⁴² The deductive approach will identify participant knowledge of key domains of hospice. The inductive approach will identify any key misconceptions or fallacies

expressed by participants in the study. The quantitative acceptability and feasibility measures will be analyzed descriptively with means and interquartile ranges. Analysis of qualitative data will be a continuous process beginning with initial interviews and continuing throughout and beyond the data generation period. All interviews will be audio-recorded and professionally transcribed verbatim. A multidisciplinary team, led by [name] will begin the analysis process with repeated readings of the transcripts to achieve immersion. The team will then develop and apply a list of codes to the transcripts using an emergent rather than a priori approach, in order to emphasize interviewee perspectives and de-emphasize team member speculations.^{43,44} All coded data will be entered into Atlas.ti v 7.0 (GmbH, Berlin) for data management. Coded transcripts will be analyzed within and across sites and settings to develop the major themes or concepts that the participants reported. The trustworthiness of study results will be enhanced through triangulation of the data and an audit trail throughout the data collection and analysis process. Following the interpretation of the qualitative findings, we will compare and contrast the results with the findings from the quantitative surveys using methods consistent with the NIH guidelines on mixed methods research.⁴⁵

Quantitative Data: We will compare differences between intervention and control using t-tests for continuous outcomes and chi-square tests for dichotomous outcomes. We will perform a multivariate analysis of our outcome variables (i.e. hospice knowledge, self-efficacy and decisional conflict) and look for mediation and/or moderation effects of age, race, and gender; while controlling for potential confounders. There is no power calculation as this is a pilot trial designed to test feasibility and acceptability.

G. Summarize Knowledge to be Gained:

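### The arms are compared with unadjusted t-tests although baseline scores on the same scales are collected; this wastes precision and leaves the one-month comparison open to bias if loss differs by arm

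*Combined protocol and SAP*

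**What the plan says.** The between-arm method is given in Section IV.E, Quantitative Data: "We will compare differences between intervention and control using t-tests for continuous outcomes and chi-square tests for dichotomous outcomes". The next sentence adds a multivariate analysis of knowledge, self-efficacy and decisional conflict. It looks for mediation or moderation by age, race and gender, "while controlling for potential confounders". The confounders are not named. The section then says: "There is no power calculation as this is a pilot trial designed to test feasibility and acceptability".

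On design, Section IV.C says "We plan to recruit 120 patients" and "This will be a patient-level trial randomized in a 2:1 intervention: control". On population, Section IV.B requires age 65 or over and a life-limiting illness, and Section IV.C adds that "we will recruit patients from both the inpatient and outpatient palliative care services", along with geriatric and primary care clinics.

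On timing, the knowledge, decisional conflict and self-efficacy scales are completed by both arms at baseline. The one-week contact is in one arm ("1 week Follow-up call (intervention only"), and "each participant (control and intervention) will be contacted at one month for the final data point collection".

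The documents state no analysis set, expected attrition, rule for death before one month, missing-data method or sensitivity analysis. The only reasons they plan to record are for not approaching an outpatient before enrolment.

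**The concern.** Two things are at stake. The first is precision. A t-test of follow-up scores ignores a baseline measurement of the same quantity that has already been paid for, in a trial of only 120 patients.

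The second is bias. Death, loss of capacity and non-response within a month are foreseeable in this population. Only the intervention arm has a hospice aid to review and an extra survey call, so loss could differ between arms in amount or in kind. If it does, and if it is related to the outcome, a comparison of responders can show a difference with no true effect, or hide a real one. Section IV.G makes positive preliminary efficacy part of the condition for moving to a multi-site trial, so the estimate will be used.

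**Working it through.** **Inputs from the documents.** 120 patients at 2:1 gives 120 × 2/3 = 80 intervention and 120 × 1/3 = 40 control. Both arms have baseline and one-month scores on the same three scales. The plan has no power, effect or attrition figure to reproduce.

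**Assumptions.** Scores in SD units; two-sided 5% test; baseline to one-month correlation r = 0.6; loss of 10% to 30% per arm; no true effect unless stated.

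**Precision with no loss.** The standard error of the unadjusted difference is √(1/80 + 1/40) = 0.194 SD. Adjustment for baseline multiplies it by about √(1 − r²) = √(1 − 0.36) = 0.80, giving 0.155 SD, a cut of about 20%. The gain depends on r: √(1 − 0.09) = 0.95 at r = 0.3 (5% cut), √(1 − 0.25) = 0.87 at r = 0.5 (13%), and √(1 − 0.49) = 0.71 at r = 0.7 (29%).

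**Bias when loss depends on the baseline score.** The responders' expected one-month mean is r times their baseline mean, so

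bias of the t-test = r × (mean baseline of intervention responders − mean baseline of control responders).

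Loss was simulated as logistic in the baseline score, with low scorers more likely to be lost. The slope is the log-odds per SD.

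| Loss, intervention vs control | Mechanism | t-test bias (SD) | t-test rejection |
|---|---|---|---|
| 20% vs 20% | same in both arms, slope 1.0 | 0.00 | 5% |
| 30% vs 20% | same in both arms, slope 1.0 | +0.05 | 5–6% |
| 30% vs 10% | same in both arms, slope 1.0 | +0.10 | 7–8% |
| 20% vs 20% | selective in intervention only, slope 1.0 | +0.10 | about 8% |
| 30% vs 20% | selective in intervention only, slope 1.0 | +0.15 | about 10% |
| 30% vs 20% | selective in intervention only, slope 1.5 | +0.19 | about 15% |

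The baseline-adjusted model has bias near zero and about 5% rejection in every row. This follows from the set-up, because loss depends only on the variable in the model.

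**If the t-test is on change scores.** The plan does not say whether follow-up or change scores are tested. For change, the multiplier is r − 1 in place of r. In the fifth row the baseline imbalance among responders is 0.15/0.6 = 0.25 SD, so the bias is (0.6 − 1) × 0.25 = −0.10 SD, with about 8% rejection. The sign reverses.

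**Opposite direction.** Take a second mechanism, in which the sickest fraction L of an arm is lost and illness has correlation ρ with the outcome. The responder mean then shifts by ρ·φ(z_L)/(1 − L). With 10% loss in intervention, 30% in control and ρ = 0.5, the bias is 0.5 × (0.1755/0.9 − 0.3477/0.7) = 0.5 × (0.195 − 0.497) = −0.15 SD. A true effect of 0.5 SD would appear as 0.35 SD, with power of 0.34 on 72 against 28 responders.

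**Limit of adjustment.** If intervention loss (30%) depends on the one-month score itself and control loss (20%) is random, the adjusted model keeps a bias of about +0.17 SD and rejects in about 15 to 17% of trials.

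**The case against.** The strongest reply is that the t-test is not the whole efficacy analysis: the very next sentence plans a multivariate analysis of the same outcomes. That stands as a fact, and a reader should not infer that an unadjusted t-test is all that is planned. But that analysis is tied to mediation and moderation, does not name baseline score, and does not say what happens to deaths or missing outcomes, so it does not settle the point.

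A reader might also infer that the plan has chosen a responders-only analysis. It has not. Section IV.E names no time point and no analysis set. The responder comparison is what the named test amounts to in practice when both arms share only the one-month follow-up.

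Nor do the documents show that loss will differ by arm. The extra call could raise retention or add burden, and the gift cards are not restricted by arm. Death and incapacity arise from illness in both arms, and equal loss by a common mechanism costs power but causes no bias. The larger figures need selection in one arm only.

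Finally, this is a pilot whose stated goal is feasibility and acceptability, and no significance threshold governs the decision to proceed. That limits the weight of the point. It does not remove it: preliminary efficacy is Aim 2, and losses by arm are themselves feasibility results.

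**Conclusion.** The point holds as a recommended change of moderate weight. The precision argument needs no assumption about loss: at a correlation of 0.6 the unadjusted test gives up about 20% in standard error, and between 5% and 29% across correlations of 0.3 to 0.7. The bias argument is conditional. For a t-test on follow-up scores, it runs from zero to about 0.19 SD across the assumed scenarios with loss related to baseline, and its direction cannot be told from the documents.

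Two stronger readings are not supported. One is that the planned comparison will be biased in favour of the aid: this needs differential loss related to outcome, for which the documents give no evidence, and a change-score test would move the other way in the same scenario. The other is that baseline adjustment cures the problem: it removes only the bias from loss related to baseline score, which is why the losses must also be reported and tested.

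**What to change.** In Section IV.E, make the main efficacy estimate for knowledge, self-efficacy and decisional conflict a linear model of the one-month score on assigned arm, whether or not the aid was viewed. Adjust for baseline score, site and setting, and report the difference with a confidence interval. The mediation and moderation analysis can stay as secondary.

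State that scores are not filled in after death. Tabulate deaths, withdrawals and non-response by arm and reason.

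Add one sensitivity analysis for patients alive at one month but without a score. If the missing scores lie δ below what the model predicts, the estimate falls by (fraction missing in intervention × δ for that arm) − (fraction missing in control × δ for that arm). For example, 30% missing in intervention with δ = 0.5 SD there and zero in control moves it by 0.30 × 0.5 = 0.15 SD. With δ = 0.5 SD in both arms at 30% and 20%, it moves by (0.30 − 0.20) × 0.5 = 0.05 SD. Report the shift at which the conclusion changes. Multiple imputation is optional.

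The cost is a few sentences, one reason-for-missing field in REDCap and modest analysis time. No patient is asked for anything more.

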Acceptability of the decision aid will be measured using the Ottawa Acceptability Scale (OAS). The OAS scale consists of 8 questions on a 5-point Likert scale with additional yes/no questions.³⁶ Feasibility will be assessed asking patients when they viewed the decision aid, if the used the paper version, the video version or both. We will also ask for input on the overall design and usefulness of the decision aid in facilitating their decisions.

Aim 2. Preliminary Efficacy:

Efficacy will be measured qualitatively and quantitatively through surveys. We are trying to determine if the decision aid improves hospice knowledge, decreases decisional conflict and improves self-efficacy.

- **Description of qualitative writing sample:** Hospice knowledge will be qualitatively assessed prior to randomization at the baseline visit to better understand the misconceptions associated with hospice care. Matsuyama et al³⁷ described a brief qualitative assessment in which participants are asked to describe “what is hospice” in their words. Participants will provide their answers on paper. These brief writings will be analyzed using thematic content analysis.

- **Knowledge of Hospice Test:** The Knowledge of Hospice Test is a 23-item scale with true/false questions.^{1,38} The Cronbach's alpha coefficient for the scale is 0.75 showing good internal reliability.
- **Decision Self-efficacy:** Is an 11-item instrument that one's self-confidence in decision making. This scale is a validated scale with a Cronbach's alpha of 0.92 and correlates with DCS subscale of being informed ($r=0.47$). Based on our prior study of a decision aid in palliative care, we hypothesize that one of the strongest effects of a decision aid might be to increase self-efficacy of the decision making.³¹

Hospice Beliefs and Attitude Scale (HBAS): The HBAS is an 8-item scale developed to measure beliefs and attitudes towards hospice care.³⁹ It has a Cronbach's $\alpha = .74$ for the scale, indicating a good degree of internal reliability.

B. Description of Population to be Enrolled:

Patients: Patients will be older adults age ≥ 65 with at least one life-limiting illness or syndrome as defined by the clinicians.

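### The plan looks for mediation by age, race and gender, which are fixed before allocation, and states no quantitative result by care setting or site

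*Combined protocol and SAP*

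**What the plan says.** **Mediation.** Section IV.E, Quantitative Data, compares the arms with t-tests and chi-square tests. It then plans a multivariate analysis of hospice knowledge, self-efficacy and decisional conflict, in which the team will "look for mediation and/or moderation effects of age, race, and gender; while controlling for potential confounders". Under Data collection in Section IV.C, "the study coordinator will collect baseline demographic and quantitative data", and only afterwards: "The research coordinator will then open the envelope".

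**Setting and site.** Section IV.E, Qualitative Data, says: "Coded transcripts will be analyzed within and across sites and settings". Of the qualitative findings it then says "we will compare and contrast the results with the findings from the quantitative surveys". On Aim 1 it says: "The quantitative acceptability and feasibility measures will be analyzed descriptively with means and interquartile ranges". No breakdown is attached to that sentence or to the survey comparison.

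Section IV.C (Settings) recruits at two health systems, from inpatient and outpatient palliative services and from geriatric and primary care clinics. The stated reason is to learn about feasibility at different points of the illness course. Section IV.G describes three points of intervention (primary care, outpatient palliative and inpatient palliative) and promises insight into when hospice should be raised.

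**The concern.** A mediator lies on the path from treatment to outcome, so the treatment must be able to change it. A decision aid cannot change a patient's age, race or gender. An estimated indirect effect through one of them therefore has no interpretation as a mechanism, yet it could be reported as one.

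The second point is an omission. Care setting is the feature around which recruitment was built, and the aid is delivered differently across settings: inpatients may use it at any time during the stay, while outpatients take it home. The feasibility questions (when the aid was viewed, and whether on paper, video or both) may well be answered differently in each. As written, the step that sets qualitative against survey findings has themes by setting on one side and no stated survey result by setting on the other.

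**Working it through.** The plan gives no power calculation, SD, alpha or dropout rate, so it has no figure of its own to reproduce beyond accrual.

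**Inputs**
- From Section IV.C: 120 patients, 2:1 allocation, 20 to 25 patients per site/setting.
- Arms: 120 × 2/3 = 80 intervention and 120 × 1/3 = 40 control.
- Cells: 2 sites × 3 settings × 20 = 120, which matches the target. Six equal cells is an assumption, because Figure 1 is not shown.
- Also assumed: outcomes in SD units, z = 1.96, no dropout, and age-outcome correlations of 0.1 to 0.3.

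**Mediation**
- Indirect effect = (arm difference in the trait) × (slope of outcome on trait). The first factor is zero in expectation, so the product is too.
- Chance imbalance in age, 95% limit: 1.96 × √(1/80 + 1/40) = 0.38 SD of age.
- Spurious indirect effect: 0.38 × 0.1 = 0.04 SD and 0.38 × 0.3 = 0.11 SD of the outcome.
- For a trait split 50/50, the imbalance limit is 1.96 × √(0.25 × (1/80 + 1/40)) = 0.19, or 19 percentage points. Divided by the trait's SD of 0.5, this is again 0.38 SD, so the same range applies at the same correlations.
- Check: 20,000 simulated trials of 80 vs 40, with a pre-allocation covariate of slope 0.3, gave a mean indirect effect of −0.0006 SD with a spread of 0.06 SD. Then 1.96 × 0.06 = 0.12, close to the upper figure.
- Differential loss by one month could add to this. The documents give no loss figure, so it is not sized.

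**Precision of a breakdown**
- Per setting: 80/3 = 26.7 and 40/3 = 13.3 patients. Per site: 40 and 20.
- Arm difference, 95% half-width:
  - overall: 0.38 SD;
  - within a setting: 1.96 × √(1/26.7 + 1/13.3) = 0.66 SD;
  - within a site: 1.96 × √(1/40 + 1/20) = 0.54 SD.
- Intervention-arm proportion near 50%, half-width 1.96 × √(0.25/n):
  - overall (n = 80): 11 points;
  - by setting (n = 26.7): 19 points;
  - by site (n = 40): 15 points.
- If 20% or 30% were lost (assumed), the within-setting arm difference becomes 0.66/√0.8 = 0.74 SD or 0.66/√0.7 = 0.79 SD.

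**The case against.** The strongest reply is that the first defect is one word. The text offers mediation and/or moderation; moderation by these traits is sound, and the team could run it alone. This is also a secondary look in a pilot with no power calculation. That limits the weight of the point but does not rescue the mediation analysis.

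On the second half, a reader might infer that acceptability and feasibility are not examined by setting at all. The documents do not support that. Aim 1 is mixed-methods, Section IV.A asks patients for input on the aid's design and usefulness, and transcripts are analysed by site and setting. Some of this content may therefore be reported by setting. The gap is confined to quantitative results.

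A reader might also infer that Aim 1 commits the trial to comparing settings. It does not: it says in whom and where the aid is tested. Nor is the step comparing qualitative and survey findings described as by setting. The support comes from the recruitment rationale in Section IV.C and the promise in Section IV.G, and even these do not specify survey data. It might be said that the undefined potential confounders include setting, but adjusting for setting does not report results by setting.

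Finally, 0.38 SD could be mistaken for the size of a spurious mediated effect. It is the imbalance in the covariate; the mediated effect is that imbalance multiplied by the age-outcome slope.

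The visit lists in Section IV.C do not name the Ottawa Acceptability Scale. That is a separate data-collection question, which affects the overall acceptability result as much as any breakdown.

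**Conclusion.** Both halves hold within these limits. Mediation by age, race and gender is wrong as written: the true mediated effect is zero, and for age chance alone could produce about 0.04 to 0.11 SD (95% limit, 80 vs 40, assumed correlations of 0.1 to 0.3). The moderation half of the sentence stands. The absence of any stated quantitative result by setting or site is a real omission given how the trial recruits and what it promises, but it is partly covered by the transcript analysis. It does not make Aim 1 unanswerable. The plan should be changed on both points. Neither affects the main two-arm comparison.

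**What to change.** 1. In Section IV.E, delete mediation for age, race and gender. Keep them as exploratory moderators or baseline covariates.
2. Add descriptive summaries with 95% CIs by care setting and by site: the quantitative acceptability and feasibility measures, and the survey outcomes by arm. Use the three care settings in Section IV.G and state where geriatric clinic patients are counted. Say that these summaries feed the comparison with the qualitative results.
3. Label them descriptive, and say that they cannot show that effects are the same or different across settings.

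The cost is analysis-plan wording: setting and site are known from recruitment, so the breakdown needs no new variable. The downside is the low precision shown above, which is why formal subgroup tests are not proposed.
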